4.2 Exclusion criteria

Patients meeting any of the following exclusion criteria are not to be enrolled in the study.

- 1) Subject is < 18 years of age or >80 years of age;
- 2) Subject is non-English speaking;
- 3) Subject is known or believed to be pregnant;
- 4) Subject is a prisoner;
- 5) Subject has impaired decision-making capacity per discretion of the Investigator;
- 6) Significant renal, cardiac or hepatic disease per discretion of the investigator;
- 7) American Society of Anesthesiologists class 4-5;
- 8) Known hypersensitivity and/or allergies to local anesthetics;
- 9) Chronic opioid use (daily or almost daily use of opioids for > 3 months at any point in their lives).
- 10) Repair of a recurrent ventral hernia
- 11) Repair of multiple ventral hernias
- 12) Unobtainable sonographic views
- 13) Lacking health insurance

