6.1 Subject identification and Screening

When seeing patients for their preoperative consult, the surgical team will identify patients to be scheduled for laparoscopic ventral hernia repair. In addition, the operating room schedule will be reviewed to identify patients scheduled for laparoscopic ventral hernia repair. The medical records for those patients will be reviewed to identify patients that meet eligibility criteria. All protected health information used during the screening process of a potential subject will be the minimum necessary for the conduct of this study. Any PHI recorded for non-eligible patients, or patients that do not meet screening requirements will be destroyed immediately.

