6.2 Recruitment and consent

For those patients meeting criteria, they will be approached by the anesthesiologist designated to care for them on the day of surgery. That anesthesiologist will then recruit the patient for the study in the pre-operative holding area. In order to ensure the candidate's privacy and confidentiality, the discussion will take place in pre-operative holding area with the cubicle's curtain and room door closed. In a tone of voice insufficient for others to overhear the conversation and in the presence of only those immediately accompanying the patient and those who are directly involved with the patient's care, the

candidate's eligibility will again be verified against the study enrollment criteria. For candidates with confirmed study enrollment eligibility, the study purpose, procedures, risks, benefits, and alternatives will then be discussed by a study staff member. The written information about the study provided to the candidate at the time of their check-in will be reviewed and they will be instructed to take up to 90 minutes to consider participation. A study member will conduct the informed consent discussion and obtain informed consent and a study physician will be available at all times for any consent-related questions. Any questions that the candidate may have will be answered. Undue coercion will be prevented by stressing that the potential subject does not have to agree to participation and that the future care of the potential subject will not change regardless of the decision about participation. If the candidate has no further questions and would like to participate, they will be asked to sign the written informed consent document.

7. Activities and measurements

Prior to the procedure:

The subject will be met in the preoperative area by a staff anesthesiologist, who interviews and examines the subject. A full explanation of general anesthesia and quadratus lumborum block, including risks, benefits, and alternatives, will be given and informed consent for anesthetic services obtained.

Subjects will be asked to rate their pain at rest using a Numerical Rating Scale (NRS) (0-10) where 0 represents no pain and 10 represents the worst pain imaginable.

Study Randomization:

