After completion of pre-operative check in and consent is obtained by the staff anesthesiologist, the subject will be randomized to receive or not receive QLB. Randomization will be determined by opening a sequential, pre-sealed envelope with the group assignment designated within. If assigned to the intervention arm, they will then be prepped for QLB.

Quadratus Lumborum Block Procedure:

The block will be performed in the preoperative holding room as is standard practice at UW Health at the American Center. An intravenous catheter will be placed, and the subject will be pre-medicated with midazolam and/or fentanyl as needed at the discretion of the staff anesthesiologist.

Quadratus lumborum blockade will be performed after positioning the patient in the lateral decubitus position with the assistance of ultrasound guidance in the mid-abdomen posterior to the mid-axillary line. A Stimuplex needle (B. Braun Medical Inc., Melsungen, Germany) will be inserted in-plane to the ultrasound probe until the tip of the needle is appropriately positioned. Thirty milliliters of 0.25% bupivacaine will be injected under ultrasound guidance after negative aspiration. The procedure will then be repeated on the opposite side, maintaining sterility and, again, injecting 30 mL of 0.25% bupivacaine. The Bupivacaine mixture will be mixed with 2.5mcg epinephrine/ml of solution as an intravascular marker which is standard in most peripheral nerve blocks. In a situation where a patient is less than 60kg, a weight-based adjustment will be made to adjust dosing to the clinically accepted standard of 0.25mg/kg of bupivacaine. In the rare event that sonographic views are unobtainable, the patient will be excluded from the study. This outcome is unlikely to be clinically significant as qualification for laparoscopic ventral hernia repair has its own cutoff for body mass index and blocks are very rarely abandoned. However, for patient safety, we reserve the right to abandon a block.

During the Surgical Procedure:

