7.2 Subject withdrawals

At any point prior to or during the intervention period, the subject's clinical care team or a study physician may decide the subject should be withdrawn from the study. Additionally, a subject may at any point elect to withdraw themselves from the study. If a subject is withdrawn from the study for any reason the subject will then be followed according to standard of care follow-up.

Study intervention will immediately stop and subject's clinical care team and a study physician will be immediately notified if the subject suffers a severe adverse perioperative outcome.

In the event the study method is terminated, the reason for termination will be documented on a case report form.

8. Data analysis and statistical considerations

All data will be summarized using standard descriptive statistics, including mean, standard deviation, minimum, maximum, median, inter-quartile range, and confidence intervals, as appropriate. The data will be presented graphically (where possible) using scatter plots, profile plots, or histograms. Data analyses will be performed on an intent-to-treat basis based upon assignment to a treatment arm using SAS (SAS Institute Inc., Cary, NC; version 8.2 or greater) or other statistical software. The primary analysis will consist of comparing the two groups for superiority. For all tests, statistical significance will be defined as a p-value less than 0.05. Repeated measures ANOVA will be used to analyze comparisons made across multiple time points. Patients with missing longitudinal data will be handled by either using data imputation methods to replace the missing data or via alternative analyses tolerant of missing data values. Holm-Bonferroni correction will be used to control familywise error rates for comparisons across multiple time points.

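### Excluding patients with unobtainable sonographic views happens, as described, after randomisation and only in the QLB arm, which contradicts the intent-to-treat analysis

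*Combined protocol and SAP*

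**What the plan says.** Section 4.2 opens with "Patients meeting any of the following exclusion criteria are not to be enrolled in the study" and lists "Unobtainable sonographic views" as criterion 12. Eligibility is checked in three ways before allocation:

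- Section 6.1, records: "The medical records for those patients will be reviewed to identify patients that meet eligibility criteria".
- Section 6.2, at recruitment: "eligibility will again be verified against the study enrollment criteria".
- Section 7, before the procedure: "The subject will be met in the preoperative area by a staff anesthesiologist, who interviews and examines the subject".

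None of these mentions ultrasound, and the schedule of activities lists no scan.

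Section 7 (Study Randomization) then has the envelope opened after consent, and continues: "If assigned to the intervention arm, they will then be prepped for QLB". Ultrasound first appears in the next subsection, the block procedure, which contains the rule "In the rare event that sonographic views are unobtainable, the patient will be excluded from the study". The text that follows plays the event down by pointing to a body mass index cutoff for the surgery and to how seldom blocks are given up. It also reserves the right to abandon a block for safety.

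Section 8 states: "Data analyses will be performed on an intent-to-treat basis based upon assignment to a treatment arm". Section 7.2 lets the care team or a study physician withdraw a subject, and section 11.1 leaves the data of subjects who withdraw prematurely out of the final study.

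**The concern.** A patient cannot be both removed from the study after allocation and analysed by allocation. As the steps are written, only QLB patients can be removed this way. A control patient with equally poor views is never scanned and stays in, so the arms analysed would no longer be the arms randomised.

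Two consequences follow.

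- **Selection.** If the removed patients would have had more pain than the others, the comparison moves in favour of QLB. If less, it moves the other way. If the same, it does not move.
- **Estimand.** If the block works, dropping unblocked patients estimates the effect in patients who can be blocked, not the assigned-arm effect that section 8 promises.

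Abandoned blocks raise a related question. Section 7 treats them together with unobtainable views, and no section says how such a patient is analysed. If the patient were handled as a withdrawal under 7.2, section 11.1 would remove the data.

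**Working it through.** **Order of events.** Records review, eligibility re-check, interview and examination, consent, envelope, block preparation in the QLB arm only, ultrasound, possible exclusion. Criterion 12 can act before the envelope only on what is already known about a patient. Anything found during the block attempt is found after allocation and in one arm. That no control is scanned is an inference, but no section describes such a scan.

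**Inputs from section 8.1.** SD 2.2 NRS, target difference 2 NRS, alpha 0.05, 80% power, 21 per arm needed, 24 per arm enrolled. Sidedness is not stated; two-sided is assumed.

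**The plan's own figure.** A two-sided two-sample t-test (noncentral t) with 2/2.2 = 0.909 gives n = 20.002, rounded up to 21 per arm. The stated 21 reproduces. The allowance is 1 − 21/24 = 12.5%. The sample size is not in question.

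**Assumptions.** The documents give neither a rate of unobtainable views nor a pain difference. I take k = 0 or 1 of 24 QLB patients excluded, which fits an event called rare, and a pain difference D of 0.5 to 2 NRS in either direction.

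**Selection shift = k × D / 24.**

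| k | D = 0.5 | D = 1 | D = 2 |
|---|---|---|---|
| 0 | 0 | 0 | 0 |
| 1 | 0.021 | 0.042 | 0.083 |

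The sign follows the sign of D. The standard error of the difference is 2.2 × √(2/24) = 0.635 NRS, so the largest shift is 0.083/0.635 = 0.13 standard errors, or 0.083/2 = 4% of the target difference.

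**Chance that it happens at all.** 1 − (1 − r)^24 for assumed rates r of 1%, 2% and 4% gives 21%, 38% and 62%.

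**Power cost of keeping the patient.** Assume that 2 NRS is the effect in blocked patients and that an unblocked patient gains nothing. With a share p = 1/24 unblocked:

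- Assigned-arm effect = 2 × (1 − 1/24) = 1.92 NRS.
- QLB-arm SD = √(2.2² + 4p(1 − p)) = 2.236.

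The right comparator is the present rule with the same patient excluded.

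| Situation | Present rule: excluded | Proposed: retained |
|---|---|---|
| No other losses | 86.2% (23 vs 24) | 83.4% (24 vs 24) |
| Three other losses per arm | 81.0% (20 vs 21) | 78.0% (21 vs 21) |

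The differences are 2.8 and 3.0 points. In the second row, if the unblocked patient is certainly among the 21 (p = 1/21, effect 2 × 20/21 = 1.90, SD 2.241), power is 77.4% and the difference is 3.6 points.

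**The case against.** The best defence is that criterion 12 makes this a pre-enrolment rule, so nobody is lost after allocation. That stands for a patient already known to have poor views, and that use of the criterion is sound. It does not rescue the sentence in the block procedure, because no described step before the envelope shows the views.

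The second defence is rarity. The protocol calls the event rare, and the body mass index cutoff for surgery acts before enrolment on both arms alike. This stands, and it limits the weight of the point. It does not say which of the two conflicting rules applies when the event occurs.

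A reader might infer that the trial is biased in favour of QLB. The documents do not support that: they give no rate, and they do not say that patients with poor views have more pain.

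A reader might also infer that patients with abandoned blocks are excluded, or, conversely, that section 8 already covers them. Neither is stated. The text runs the two events together and is silent on how abandoned blocks are analysed.

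Finally, the dilution figures treat 2 NRS as the effect in blocked patients. Section 8.1 gives it as the meaningful difference between groups and does not say this. The power cost is therefore conditional on that reading.

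**Conclusion.** The contradiction is real and can be read directly from sections 7 and 8: an exclusion that, as described, is post-randomisation and one-armed, against an analysis by assigned arm. Criterion 12 does not cure it, and the handling of abandoned blocks is left open, with a possible route to data loss through 7.2 and 11.1.

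The expected numerical effect is small: 0 to 0.08 NRS, at most 0.13 standard errors, sign unknown, under the assumed 0 or 1 of 24 and a pain difference of up to 2 NRS. It should be fixed because the text would otherwise leave the choice between two rules until after an assignment is known, not because a large bias has been shown.

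**What to change.** 1. In section 7 (block procedure), replace the exclusion sentence with: *A randomised patient in whom sonographic views are unobtainable, or whose block is abandoned, stays in follow-up and is analysed in the assigned arm; the number of such patients is reported.*
2. In section 4.2, add to criterion 12: *applies only on information available before the envelope is opened.*
3. In section 7.2, add: *Not completing the block is not in itself a withdrawal.* Section 11.1 then does not remove these data.

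The freedom to abandon a block is unchanged.

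The cost is an amendment with written IRB approval (section 12.6) and, under the stated assumptions, about 3 points of power with one such patient. After three other losses per arm, power would be slightly below 80%.

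Assessing views in every consented patient before the envelope is opened would also reconcile criterion 12 with section 8. It adds a scan for every control patient, and the analysis of abandoned blocks would still have to be stated.

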10.1 Adverse event definitions	15
10.2 Severity assessment	16
10.3 Causality assessment	16
10.4 Procedures for recording and reporting adverse events	16
10.5 Other reportable events	16
11. Trial safety monitoring	17
11.1 Data Safety Monitoring Committee	17
12. Administrative requirements	18
12.1 Good clinical practice	18
12.2 Data quality assurance	18
12.3 Study monitoring	18
12.4 Ethical consideration	18
12.5 Patient confidentiality	18
12.6 Investigator compliance	18
12.7 Subject cost and payment	19
13. Funding sources	19
14. Publication Policy	19
References	20

Schedule of activities

	Screening/ Recruit/ Procedure Visit 1	PACU Visit 2	24 hours Post-op Visit 3	48 hours Post-op Visit 4 (Inpatient/ Phone)	7 days Post-op Visit 5 (Phone)
Window	Morning of Surgery	Following surgical procedure	24 hours post-op +/- 6 hours	48 hours post-op +/- 6 hours	7 days post-op +/- 6 hours
Screening and Eligibility	X				
Informed Consent	X				
Demographics	X				
Medical History	SOC				
Randomization	X				
Quadratus Lumborum Block	X				
Standard Medical Management	SOC				
Numbness Testing ¹		X			
Pain Questionnaire ²		X	X	X	X
Concomitant Medications ³	SOC	X	X	X	X
Adverse Events	SOC	SOC	X	X	X

¹Temperature sensation will be examined using a cold sensory technique

² Pain at rest, pain with activity, opioid consumption, nausea, location of most severe pain and satisfaction with regional anesthesia technique will be assessed

³Medications that are taken at home regularly and prior to arrival on the day of surgery, surgery premedication, and all medications for nausea and pain will be recorded.

List of abbreviations and definitions

AE	Adverse event
DSMC	Data Safety Monitoring Committee
PACU	Post-Anesthesia Care Unit
POD	Post-Operative Day
QLB	Quadratus Lumborum Block
SAE	Serious Adverse Event

1. Introduction

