1.2 Rationale and hypothesis

Thousands of patients undergo ventral hernia surgery each year. Quadratus lumborum blocks are a relatively new approach for providing analgesia to the abdominal wall. The effectiveness of quadratus lumborum blocks in reducing pain, opioid consumption, and time to discharge has not been evaluated for this surgery. We propose a prospective, single-center, randomized trial to evaluate the impact of quadratus lumborum block on patient recovery profile when performed for laparoscopic ventral hernia repair compared to a standard medical management. Standard medical management typically includes perioperative multimodal analgesia utilizing acetaminophen, opioids, non-steroidal anti-inflammatory drugs, and dexamethasone. Peripheral nerve blocks, as are offered in our study, are typically offered to patients but are not routinely performed secondary to time constraints in the operating room and surgeon or patient preference. The primary outcome of the study is pain at rest on POD1. Secondary outcomes will include pain at rest on POD 0, 2 and 7, pain with activity on POD 0, 1, 2 and 7; opioid consumption on POD 0, 1, 2 and 7; nausea in PACU; time to hospital discharge and patient satisfaction.

2. Objectives

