2.2 Secondary outcomes and endpoints

The secondary outcomes of this study are to compare the following perioperative variables:

Preoperative Variables:

- Baseline pain

Intraoperative Variables:

- Opioid consumption
- Additional analgesics
- Anti-emetic administration

PACU Variables:

- Pain at rest
- Pain with activity
- Nausea
- Numbness distribution
- Opioid consumption
- Time in PACU (duration)
- Time to discharge home (duration)
- Location of most severe pain

POD 1, 2, and 7 Variables:

- Pain at rest

- Pain with activity
- Opioid consumption in morphine equivalents
- Nausea necessitating treatment
- Location of most severe pain
- Satisfaction with perioperative care

3. Study design

This study is a prospective, single-center, randomized trial in which 48 subjects will be enrolled at the University of Wisconsin Hospitals and Clinics (UWHC). The details of the power analysis can be found below. These subjects must meet study eligibility criteria and be scheduled to undergo an elective laparoscopic ventral hernia repair. These subjects must also agree to undergo quadratus lumborum block for postoperative analgesia. Patients will be randomized to receive QLB in addition to medical management or medical management alone. Recovery characteristics, including pain scores, nausea, opioid consumption, duration of time in PACU and to discharge, will be evaluated.

4. Study population

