4.3 Protected populations

Prisoners

Due to the complexity of state and federal requirements governing the participation of prisoners in research, patients who are prisoners will not be considered for participation in this trial. In the unlikely event that a subject becomes a prisoner while participating in this trial, study procedures will stop and the subject will be returned to the clinical mode used prior to the intervention period or, if desired, an alternate mode requested by the clinical care team.

Pregnancy

Patients who are known to be pregnant will be excluded from participation.

5. Trial interventions

The intervention portion of this study is the randomized assignment (1:1) to receive quadratus lumborum block plus medical management or standard medical management alone. Randomization will be accomplished using an online service (www.randomizer.org) and prefilling sealed envelopes determining each subject's intervention group. Randomization will occur immediately prior to surgery. In all other aspects, the subject will receive the standard of anesthesia care appropriate for their surgery as determined by the primary anesthesia team caring for the subject. Preoperative medications will be left at the discretion of the in-room anesthesiologist for both pain and nausea regardless of the intervention.

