In the operating room and in the procedural suite, monitors will be applied to the subject per established American Society of Anesthesiology (ASA) guidelines. At a minimum, these include non-invasive monitoring of blood pressure by automated cuff, oxygen saturation via pulse oximetry, heart rate and rhythm by 5-lead continuous electrocardiographic (ECG) tracing, core body temperature and expired carbon dioxide concentration. Additional monitoring may be applied on a case-by-case basis as deemed appropriate by the attending anesthesiologist. General anesthesia will be induced and endotracheal intubation will be performed by the in-room anesthesia team. Anesthetic care, including analgesics and antiemetics, will be administered per their discretion and extracted from the medical record.

Post-Procedure:

The patient will be visited in the PACU to assess pain satisfaction with perioperative care. Additionally, the following standard of care assessments will be completed: pain, opioid consumption, nausea, duration of PACU stay, and location of most severe pain. This information will be ascertained by questioning the patient and reviewing the subject's medical record.

For patients that underwent QLB, numbness to ice will be assessed. For this assessment, a plastic glove filled with ice water will be used to systematically assess for numbness too cold in the thoracic and lumbar dermatomes.

Postoperative analgesia will generally consist of scheduled acetaminophen, scheduled ibuprofen, oxycodone or hydrocodone PRN or any combination of these. Therapy may be altered for patients with history of drug intolerances or allergies or any other contraindication to a specific therapeutic agent. Analgesic therapy represents standard of care and is not altered by study involvement.

24 hours, 48 hours, and 7 days post-operative follow-up:

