The patient will be contacted via phone at 24 hours, 48 hours, and 7 days to assess satisfaction with regional anesthesia, pain at rest, pain with activity, opioid consumption, nausea, pain disturbing sleep, and location of most severe pain. Duration of hospitalization will be obtained from review of medical record. Subjects with new or persistent complaints at 7 days post-surgery that could be related to the study procedures will be offered continued follow-up by telephone. Follow-up procedures would depend greatly on the clinical presentation but could include imaging, specialist consultation or surgical intervention. Subjects without complaints will be given appropriate information for contacting the research team if such complaints arise.

Concomitant Medications:

Analgesic and anti-emetic requirements for block placement, intraoperatively, and in PACU will be extracted from the patient's electronic medical record.

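### Satisfaction on POD 1, 2 and 7: the listed endpoint is satisfaction with perioperative care, but the follow-up text collects satisfaction with regional anesthesia, which controls do not receive

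*Combined protocol and SAP*

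**What the plan says.** The combined protocol and SAP refers to patient satisfaction in five places.

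- **Section 2.2, POD 1, 2 and 7 variables:** "Satisfaction with perioperative care". The list opens with "The secondary outcomes of this study are to compare the following perioperative variables".
- **Section 7, follow-up at 24 hours, 48 hours and 7 days:** "The patient will be contacted via phone at 24 hours, 48 hours, and 7 days to assess satisfaction with regional anesthesia".
- **Schedule of activities, footnote 2**, which defines the pain questionnaire given in PACU and at all three follow-up contacts: "location of most severe pain and satisfaction with regional anesthesia technique will be assessed".
- **Section 7, Post-Procedure (PACU visit):** "The patient will be visited in the PACU to assess pain satisfaction with perioperative care".
- **Section 1.2**, closing the list of secondary outcomes: "time to hospital discharge and patient satisfaction".

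On treatment, Section 5 randomizes patients 1:1 "to receive quadratus lumborum block plus medical management or standard medical management alone". Section 9.1 describes standard care for this operation as not including a regional technique.

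**The concern.** Satisfaction with the whole of perioperative care is something every patient can rate. Satisfaction with a regional anesthetic can be rated only by someone who had one. The endpoint section names the first, and both passages that tell staff what to collect at the matching times name the second.

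If staff follow the collection text, there are two possible results.

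- **Controls leave the item blank.** The data are then missing for a whole arm by design. Section 8 offers imputation, or analyses that tolerate missing values, for incomplete longitudinal data. Neither means anything when one arm had nothing to rate.
- **Controls answer anyway.** They are rating a procedure they did not receive, having agreed to it at enrolment (inclusion criterion 3). Their answers may reflect their reaction to the allocation and not the care they had.

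Either way the between-arm comparison of this endpoint is lost. Satisfaction is patient-reported at fixed times and is not among the items that Section 7.1 extracts from the medical record, so a wrongly worded question cannot be put right afterwards.

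**Working it through.** **1. Wording by time point**

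| Time point | Endpoint in Section 2.2 | Collected per Section 7 | Collected per footnote 2 |
|---|---|---|---|
| PACU | none listed | perioperative care | regional technique |
| 24 h (POD 1) | perioperative care | regional anesthesia | regional technique |
| 48 h (POD 2) | perioperative care | regional anesthesia | regional technique |
| 7 days (POD 7) | perioperative care | regional anesthesia | regional technique |

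At all three times where Section 2.2 lists the endpoint, neither collection passage names it, and no other passage collects it then. The two collection passages also disagree with each other in PACU, but no satisfaction endpoint is listed there.

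**2. Is the follow-up item limited to block patients?** Not in the text. Section 7 does state such a limit for the other block-specific assessment: "For patients that underwent QLB, numbness to ice will be assessed". The follow-up paragraph, in the same section, has no equivalent and refers simply to the patient.

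**3. Could the two phrases be synonyms?** The protocol uses both, and Section 7 alone uses one in PACU and the other at follow-up. For a control patient the two cannot mean the same thing.

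**4. Group sizes.** Section 8.1 gives 21 per group, raised to 24 for dropout. With a difference of 2, SD 2.2, alpha 0.05 (two-sided assumed, since the text does not say) and 80% power:

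- A two-sample t-test solves to n = 20.0016, which rounds up to 21; power at 21 is 0.820. The normal approximation gives 19.
- Implied dropout is (24 − 21)/24 = 12.5%, and 21/(1 − 0.125) = 24.

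The stated figures reproduce and do not depend on the satisfaction wording.

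**5. Assessments affected, if the questionnaire copies the protocol wording**

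| | Control arm | Both arms | Control share |
|---|---|---|---|
| As planned | 24 × 3 = 72 | 48 × 3 = 144 | 72/144 = 50% |
| After all allowed dropout | 21 × 3 = 63 | 42 × 3 = 126 | 63/126 = 50% |

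If the questionnaire already uses arm-neutral wording, the number affected is 0.

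**The case against.** The strongest reply is that the harm depends on a form nobody can inspect here. The case report form (Section 7.1) and the follow-up questionnaire (Section 10.1) are not in the documents. If they ask about perioperative care, what remains is a labelling error. The intended endpoint can also be read from Section 2.2 and the PACU paragraph, although that PACU sentence is itself garbled. This stands as a limit on the consequence. It does not remove the contradiction, because staff making the calls would work from the follow-up paragraph.

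Four smaller objections:

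- **The list in Section 2.2 is not purely comparative.** It also contains numbness distribution, which is tested only in block patients. That is true, but Section 7 states that restriction, and satisfaction with perioperative care plainly applies to both arms.
- **Silence in footnote 2 shows little.** The schedule puts no arm limit on numbness testing either. This is correct; the contrast has force only within Section 7.
- **Section 1.2 is not in conflict.** Its wording is generic and fits either reading. This is accepted, so an edit there is optional.
- **The counts measure neither bias nor lost information.** The 50% share follows from 1:1 allocation, and 63 and 126 apply only if all the allowed dropout occurs. This is also accepted; the counts show the extent of the problem and nothing more.

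**Conclusion.** The concern holds. The protocol contradicts itself on what is measured for one secondary endpoint, at all three of its listed time points, and the version it tells staff to collect does not apply to the control arm. Followed as written, it gives no valid comparison of that endpoint between arms.

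The extent is 63 to 72 control assessments if the questionnaire mirrors the protocol text, and none if it is already arm-neutral. Confidence in the textual contradiction is high; the loss of the comparison is conditional on the unseen questionnaire. The primary outcome (resting NRS on POD 1) and the sample size are unaffected. This should be corrected, but it does not threaten the main result.

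**What to change.** 1. In the Section 7 follow-up paragraph and in schedule footnote 2, replace the regional-anesthesia wording with the Section 2.2 term, "Satisfaction with perioperative care".
2. Check the case report form and follow-up questionnaire. If needed, change the item so that it is worded identically in both arms.
3. If a block-specific satisfaction item is wanted, ask it only of patients who received the block, and report it descriptively.
4. Optionally, use the same name in Section 1.2.

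The cost is two protocol phrases (three with Section 1.2) and at most one questionnaire item. No extra visits, staff or patients are needed. The check should come before further follow-up calls, since answers to the wrong question cannot be converted later.
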